## 6.3. Measures to Minimize Bias: Randomization and Blinding

### Randomization and stratification

All participants will be centrally randomized and assigned to LY3209590 or insulin glargine using an IWRS. Before the study is initiated, the login information and directions for the IWRS will be provided to each site.

Participants will be randomly assigned in a 1:1 ratio to LY3209590: insulin glargine.

Participants will be stratified based on

- country
- HbA1c stratum (<8% and  $\geq$ 8%) at Visit 1
- Routine use of personal CGM or FGM at randomization (yes/no)

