### **9.3.3. Secondary Endpoints Analysis**

#### **9.3.3.1. Multiplicity Adjusted Endpoints**

A graphical approach will be used to control the overall type I error for the primary objective and testing the superiority of LY3209590 compared with insulin glargine for

- 1) change in HbA1c from baseline at Week 26
- 2) the percentage of participants achieving HbA1c <7% at Week 26 without nocturnal hypoglycemia (<54 mg/dL [3.0 mmol/L] or severe) during treatment phase up to Week 26
- 3) the event rate of participant-reported clinically significant nocturnal hypoglycemia (<54 mg/dL [3.0 mmol/L] or severe) during treatment period up to Week 26

The superiority test in change from baseline at Week 26 in HbA1c will be based on the same primary endpoint analysis described above.

The percentage of participants achieving HbA1c <7% at Week 26 without nocturnal hypoglycemia (<54 mg/dL [3.0 mmol/L] or severe) will be analyzed by logistic regression model including treatment, strata (country and use of personal CGM or FGM), baseline HbA1c value, and baseline incidence of nocturnal hypoglycemia as independent variables.

The rate of nocturnal hypoglycemia will be analyzed by a negative binomial regression with treatment, baseline HbA1c, baseline incidence of nocturnal hypoglycemia as independent variables, and log (exposure in year) as the offset.

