**Secondary estimands (for multiplicity-adjusted objectives)**

The superiority test in change from baseline to Week 26 in HbA1c will also be based on the primary estimands described above.

The percentage of participants achieving HbA1c <7% at Week 26 without nocturnal hypoglycemia (<54 mg/dL [3.0 mmol/L], or severe) during treatment phase up to Week 26 will be based on a composite estimand. Section 4.4.1.2 contains additional details.

The participant-reported clinically significant nocturnal hypoglycemia (<54 mg/dL[3.0 mmol/L], or severe) is 1 of the safety measures for the study. The event rate will be based on all available data during the specific analysis period. Relative rate between randomized treatment groups will be used for treatment comparison.

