Analysis Model	
After the imputation, the observed and imputed data will be analyzed by the ANCOVA model using treatment, strata (country, routine use of personal CGM or FGM at randomization), and baseline value of the dependent variable as independent variables. The statistical inference will be based on the multiple imputation framework by Rubin (1987).
	
The MMRM model will include treatment, strata (country, and routine use of personal CGM or FGM at randomization), visit and treatment-by-visit interaction as fixed effects, and baseline value of the dependent variable as a covariate. The Kenward-Roger approximation will be used to estimate denominator degrees of freedom for the MMRM models. An unstructured covariance structure will be used to model the within-participant errors. If this structure fails to converge, the following covariance structures will be used in order until one converges:
 
 
1. Toeplitz with heterogeneity
 
2. Autoregressive with heterogeneity
 
3. compound symmetry with heterogeneous variances
 
4. Toeplitz
 
5. Autoregressive
 
6. Compound symmetry without heterogeneous variances.
 

Abbreviations: ANCOVA = analysis of covariance; CGM = continuous glucose monitoring; EAS1 = efficacy analysis set 1; EAS2 = efficacy analysis set 2; FGM = flash glucose monitoring; HbA1c = hemoglobin A1c; MMRM = mixed model repeated measurement.

The 2-sided 95% CI of the LS mean difference (LY3209590 – insulin glargine) in the HbA1c (in %) change from baseline at Week 26 (Visit 23) will be estimated. For both estimands, LY3209590 will be declared noninferior to insulin glargine if the upper limit of the 2-side 95% CI for the LS mean difference in the HbA1c change from baseline is below NIM of +0.4%. In addition, the 95% CI for the LS mean difference will be compared to an alternative NIM of +0.3%.

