### **4.4. Secondary Endpoints Analysis**

#### **4.4.1. Key Secondary Endpoints**

A graphical approach will be used to control the overall type I error for the primary objective and the key secondary objectives. The key secondary objectives will test the superiority of LY3209590 compared with insulin glargine for the following endpoints.

- 1) change in HbA1c from baseline at Week 26 (Visit 23)
- 2) the percentage of participants achieving HbA1c <7% at Week 26 without nocturnal hypoglycemia (<54 mg/dL [3.0 mmol/L] or severe) during treatment phase up to Week 26 (Visit 23), and
- 3) the event rate of nocturnal hypoglycemia (<54 mg/dL or severe) during the treatment phase up to Week 26 (Visit 23).

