Analysis model	The composite endpoint will be analyzed using a logistic regression model including treatment, strata (country and routine use of personal CGM or FGM at randomization), baseline HbA1c value, and baseline incidence of nocturnal hypoglycemia. Odds ratio (LY3209590 vs. insulin glargine) and 95% confidence interval, and p-value will be used for treatment comparison. Multiple imputation will be performed, and the statistical inference will be based on the multiple imputation framework by Rubin (1987).	Same model as for treatment regimen estimand

The rate of participant-reported nocturnal hypoglycemia (<54 mg/dL [3.0 mmol/L] or severe) will be analyzed by a negative binomial regression. The analysis details are provided in Section [4.6.2.2.1](#).

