Event rate of Level 1 hypoglycemic events (events/participant/year): • All documented	Baseline, 0-6, 0-12, 0-26, 12-26 weeks, post-treatment period	Negative binomial regression with treatment, baseline HbA1c and baseline Level 1 hypoglycemia rate as covariates, log (exposure/365.25 days) as the offset in the model.
Event rate of Level 2 hypoglycemic events (events/participant/year): • All documented	Baseline, 0-6, 0-12, 0-26, 12-26 weeks, post-treatment period	Negative binomial regression with treatment, baseline HbA1c and baseline Level 2 hypoglycemia rate as covariates, log (exposure/365.25 days) as the offset in the model.

Endpoint	Analysis Period	Statistical Method
Event rate of Level 3 hypoglycemic events (events/participant/year): 
 
• All documented
 
	Baseline, 0-26 weeks, post-treatment period	Negative binomial regression with treatment, baseline Level 3 hypoglycemia rate and baseline HbA1c as covariates, log (exposure/365.25 days) as the offset in the model.  If the number of events is too small to run the negative binomial regression, exposure adjusted rate calculated by total number of events divided by total exposure for individual patients) will be provided and the empirical method (see Appendix 11 (Section 6.11) for details) will be used for treatment comparison.
Event rate of Level 2/3 hypoglycemic events (events/participant/year): 
 
• All documented
 
• Nocturnal
 
• Non-nocturnal
 
	Baseline, 0-6, 0-12, 0-26, 12-26 weeks, post-treatment period	Negative binomial regression with treatment, baseline HbA1c and baseline hypoglycemia rate of the same hypoglycemia type as covariates, log (exposure/365.25 days) as the offset in the model.  The plots of the mean cumulative functions (MCFs) by each treatment arm will also be created. The population mean for cumulative number of events up to time t, $M(t)$ , will be estimated using a nonparametric estimation method described by Nelson (2003).
Incidence of Level 1 hypoglycemic events: 
 
• All documented
 
	Baseline, 0-6, 0-12, 0-26, 12-26 weeks, post-treatment period	Logistic regression with treatment, baseline HbA1c and baseline Level 1 hypoglycemia incidence as covariates.

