#### 4.6.2.2.2. Hypoglycemic Events derived from CGM

Level 2, Level 2 ending with BG value  $\geq 70$  mg/dL, and Level 1 or Level 2 hypoglycemic events collected from the sponsor provided CGM are defined in Appendix 6, Section 6.6.2. The analysis for incidence, event rate, and duration are described in the table below. All data are included in the analysis. Missing data will be handled as described in Appendix 6.

Endpoint	CGM Session*	Statistical Method
Event rate of Level 1 or Level 2 hypoglycemic events (events/participant/year): 
 
• 24-hour
 
	Baseline, 0-4, 8-12, 22-26, 0-26 weeks, post-treatment period	Negative binomial regression with treatment, baseline HbA1c and baseline Level 1 or Level 2 hypoglycemia rate as covariates, log (exposure/365.25 days) as the offset in the model.
Event rate of Level 2 hypoglycemic events (events/participant/year): 
 
• 24-hour
 
	Baseline, 0-4, 8-12, 22-26, 0-26 weeks, post-treatment period	Negative binomial regression with treatment, baseline HbA1c and baseline Level 2 hypoglycemia rate as covariates, log (exposure/365.25 days) as the offset in the model.

Endpoint	CGM Session*	Statistical Method
Event rate of Level 2 hypoglycemic events ending with $\geq 70$ mg/dL (events/participant/year): • 24-hour	Baseline, 0-4, 8-12, 22-26, 0-26 weeks, post-treatment period	Negative binomial regression with treatment, baseline HbA1c and baseline rate for Level 2 hypoglycemia ending with $\geq 70$ mg/dL as covariates, log (exposure/365.25 days) as the offset in the model.
Incidence of Level 1 or Level 2 hypoglycemic events: • 24-hour	Baseline, 0-4, 8-12, 22-26, 0-26 weeks, post-treatment period	Logistic regression with treatment, baseline HbA1c and baseline Level 1 or Level 2 hypoglycemia rate as covariates.  The total number of episodes, number of episodes that includes Level 2 hypoglycemia episodes, and number of episodes that include glucose readings $<54$ mg/dL(3.0 mmol/L) but no Level 2 hypoglycemia episodes will be summarized for each CGM session.
Incidence of Level 2 hypoglycemic events: • 24-hour	Baseline, 0-4, 8-12, 22-26, 0-26 weeks, post-treatment period	Logistic regression with treatment, baseline HbA1c and baseline Level 2 hypoglycemia incidence as covariates.

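### The model for the controlled nocturnal hypoglycemia rate leaves out routine personal CGM/FGM use, a randomization stratum; adding it is a near-costless, low-severity improvement

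*SAP*

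**What the plan says.** Protocol 6.3 and SAP 1.2 name three stratification factors: country, screening HbA1c (below 8%, or 8% and above), and "Routine use of personal CGM or FGM at randomization (yes/no").

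Three endpoints are tested for superiority under type I error control. They are HbA1c change, the composite of HbA1c below 7% without nocturnal hypoglycemia, and "the event rate of nocturnal hypoglycemia (<54 mg/dL or severe) during the treatment phase up to Week 26 (Visit 23") (SAP 4.4.1). Their models treat the strata differently:

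- HbA1c (SAP 4.3.2): "the ANCOVA model using treatment, strata (country, routine use of personal CGM or FGM at randomization"), plus baseline value. The MMRM for the efficacy estimand carries the same two strata.
- Composite (SAP 4.4.1.2): "logistic regression model including treatment, strata (country and routine use of personal CGM or FGM at randomization"), plus baseline HbA1c and baseline incidence of nocturnal hypoglycemia.
- Nocturnal rate (SAP 4.6.2.2.1): "Negative binomial regression with treatment, baseline HbA1c and baseline hypoglycemia rate of the same hypoglycemia type as covariates", with a log-exposure offset. Protocol 9.3.3.1 has the same structure: "The rate of nocturnal hypoglycemia will be analyzed by a negative binomial regression with treatment, baseline HbA1c, baseline incidence of nocturnal hypoglycemia".

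Baseline HbA1c covers the HbA1c stratum. CGM/FGM use and country are both absent from the rate model. SAP 1.1 says that this endpoint "is 1 of the safety measures for the study", and the other hypoglycemia rate models are built alike. For CGM-derived events, for example, SAP 4.6.2.2.2 has "Negative binomial regression with treatment, baseline HbA1c and baseline Level 1 or Level 2 hypoglycemia rate as covariates". CGM/FGM use enters a nocturnal rate model only in the subgroup analysis of SAP 4.7.2.2, as a factor with a treatment interaction. That leaves the controlled test unchanged.

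**The concern.** A factor used to stratify the randomization is normally carried into the analysis, above all for a confirmatory test. Here two of the three controlled superiority endpoints follow that rule for CGM/FGM use and the third does not, without explanation. The nocturnal rate is also the only hypoglycemia rate model that carries a controlled test.

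CGM/FGM use could plausibly be related to this outcome. Events come from participants' e-diary entries and study-glucometer readings (SAP 4.4.1.1). Participants who already had a personal CGM may keep it, and must check a blood glucose before treating a low that it indicates (protocol 8.1.1.2). Users and non-users may therefore differ in how often a night-time low is recorded. The documents give neither the size nor the direction of any difference.

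Only precision is at stake. Stratified randomization balances the factor between arms. With a log link and no interaction, the rate ratio is the same within strata and overall, so leaving the term out does not shift the estimate.

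**Working it through.** **Inputs from the documents.** 284 participants per arm; rates of 0.55 and 1.1 events per participant-year, each with SD 2.6; alpha 0.05 (SAP 5). The test is 2-sided (protocol 9.3.1). Treatment lasts 26 weeks, taken as t = 0.5 year.

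**The plan's own power figure.** SAP 5 states about 83%. For a negative binomial rate ratio, Var(log RR) = (1/n)[1/(r₁t) + 1/(r₀t) + 2k], with k = (SD² - r)/r².

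- Dispersion from the glargine arm: k = (2.6² - 1.1)/1.1² = 5.66/1.21 = 4.68.
- Variance = (3.636 + 1.818 + 9.355)/284 = 0.0521, so SE = 0.228.
- Power = Φ(0.693/0.228 - 1.96) = 85.9%.
- The same k formula for LY3209590 gives (2.6² - 0.55)/0.55² = 20.5. A delta-method calculation using both stated SDs gives 59.9%.
- With k = 4.68, a mean exposure of 0.40 year gives 82.8% and 0.425 year gives 83.7%.

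SAP 5 states neither a common dispersion nor an exposure, so 83% is under-specified and was not reproduced. The present point does not depend on it.

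**Effect of adding the term.** Assumptions, none of them in the documents: user share 10%, 30% or 50%; user event rate 0.5 to 3 times that of non-users; equal arm split within the stratum. Each setting has 4000 simulated trials with maximum-likelihood fits. Model terms are treatment, baseline HbA1c (no assumed effect) and a baseline rate from a 14-day lead-in that shares the participant's frailty, with and without CGM/FGM use. Total dispersion is held at 4.68 within each setting, so only differences within a row should be read.

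Results with 30% users:

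| User rate vs non-user | Power without, with | Mean model SE without, with | SE change |
|---|---|---|---|
| 0.5x | 88.1%, 88.5% | 0.2190, 0.2179 | -0.5% |
| 1x | 87.6%, 87.6% | 0.2213, 0.2215 | +0.1% |
| 1.5x | 88.2%, 88.2% | 0.2197, 0.2194 | -0.1% |
| 2x | 89.2%, 90.1% | 0.2172, 0.2157 | -0.7% |
| 3x | 89.7%, 91.0% | 0.2127, 0.2083 | -2.1% |

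At 1x, 2x and 3x the power change is -0.2, +0.3 and +0.4 points with 10% users, and 0.0, +0.3 and +1.2 points with 50% users. Over all settings the range is -0.2 to +1.3 points (Monte Carlo SE 0.12 to 0.28).

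**Type I error** (1.1 per year in both arms, 30% users), without and with the term: 6.3% and 6.2% at 1x, 6.5% and 6.0% at 2x, 6.5% and 6.4% at 3x (Monte Carlo SE about 0.4). Both models run above 5%, so the powers are not size-adjusted. The term does not add to the excess.

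**Unequal dispersion** (4.68 and 20.5, 30% users). Power without the term is 77.8% to 81.3%, and the change is +1.0 to +1.7 points. The change is +1.5 even at 1x, where the term has no effect. The fitted common-dispersion SE (0.24 to 0.26) is also below the empirical SD (0.29 to 0.32). This shows no loss; it should not be read as a gain.

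**Cross-checks.** A smaller simulation (1000 to 1500 trials per setting, no baseline covariates, user share 20% to 50%, user rate 0.5 to 4 times) gave -0.8 to about +2.5 points under common dispersion, mostly within Monte Carlo error of about 1 point. The mean log rate ratio agreed to within 0.004. A further run (30% users, dispersion 4.68) gave 86.8% to 86.9% at 1x, 88.1% to 88.9% at 2x and 89.3% to 90.7% at 3x. The extra degree of freedom is set against about 284 × 0.5 × (1.1 + 0.55) = 234 expected events.

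**The case against.** The case for leaving the model alone has several parts.

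- **The benefit is not established.** With 30% users the change is nil at 1x and 1.5x, and it nears 1 point only if users have two or more times the non-user rate. Under the two stated SDs no gain can be claimed. Protocol exclusion criterion 18 bars planned changes in CGM/FGM use, so a stable user effect would also act at baseline and be partly absorbed by the baseline rate. All this stands, and it is why the point is rated low.
- **Gating.** SAP 2.1 tests in sequence. If the order is that of SAP 4.4.1 (the figure is not shown), a gain counts only after HbA1c superiority and the composite have both succeeded. This stands and lowers the practical value further.
- **Consistency is only partial.** Country would still be missing, so the model would match neither the other controlled models nor the other rate models. This also stands. Country has many levels and is not equally cheap to add; it was not simulated.
- **It is a safety convention.** This is weaker. The CGM hypoglycemia duration models in SAP 4.6.2.2.2, also safety analyses, do adjust for CGM/FGM use. So do the uncontrolled DID-EQ and EQ-5D-5L analyses (SAP 4.4.2.3.1 and 4.5.3.2).
- **The change reaches further than one line.** SAP 4.7.2.2 builds its subgroup models from the same covariates, and one table row in SAP 4.6.2.2.1 covers three event types and several periods. This is true but harmless, and wording can settle it.
- **Timing.** SAP version 2 was approved on 18 March 2024, and the documents do not show whether the data are still blinded. The recommendation is therefore conditional on that.

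**Conclusion.** The omission is real and unexplained, and its severity is low. There is no bias, validity problem or power shortfall. Under common dispersion of 4.68, adding the term changes power by -0.2 to +1.3 points and costs 0.1% in standard error when it has no effect. The size of any gain rests entirely on the assumed share of users and their assumed event rate. What does not depend on a favorable assumption is the low risk: no material loss of precision and no rise in type I error appeared in any setting. For a confirmatory test, an already collected stratification factor is worth including on those terms.

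**What to change.** Before unblinding, add routine personal CGM/FGM use at randomization (yes/no) as a covariate in the negative binomial model for the nocturnal Level 2/3 rate in SAP 4.6.2.2.1. Give the nocturnal rate its own row, because the present row also covers the all-documented and non-nocturnal rates. State that the term applies to the controlled 0-26 week analysis, and say whether the other periods and the subgroup models of SAP 4.7.2.2 take it on. The other hypoglycemia models need not change.

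Record the change from protocol 9.3.3.1 in the Version History, as SAP 4.9 provides. The same entry could note that the protocol adjusts for baseline incidence and the SAP for baseline rate, a difference not listed there now.

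The cost is one degree of freedom, one model line and one Version History entry, with no change in sample size or alpha. Protocol 9.3.1 and SAP 4.1 require an amendment only when a principal feature of the protocol changes, so none is shown to be needed. After unblinding, the adjusted model could serve only as a labeled sensitivity analysis.

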Basal/total insulin dose ratio	
The baseline period is the screening/lead-in period prior to the initiation of study treatment.
 
See detailed derivation of variables in Section 4.4.2.1.
	
All scheduled visits after Week 0 (Visit 3) and up to Week 26 (Visit 23) in EAS2 for MMRM.
 
See detailed derivation of variables in Section 4.4.2.1.

Fasting glucose by SMBG	
The baseline period is the lead-in period up to the day of first dose of study treatment. Baseline will be derived as the average of all fasting glucose measurements between V2 date and the first dose date.
	
All available data after the day of first dose of study treatment up to Week 26 (Visit 23) in EAS2 for MMRM.
 
Values at each visit will be derived as average of all fasting glucose measurements from the day post prior visit up to the day of the next visit.
 
Data at Week 26 (Visit 23) in EAS1 for ANCOVA with multiple imputation for missing data.

Analysis	Baseline Observations	Post-Baseline Observations
Fasting serum glucose	The baseline is the last non-missing assessment prior to or on the day of the first dose of study treatment.	
All scheduled visits after the day of first dose up to Week 26 (Visit 23) for MMRM
 
Planned measurements at scheduled visits will be included.
 
Data at Week 26 (Visit 23) in EAS1 for ANCOVA with multiple imputation for missing data.

Participant-reported hypoglycemia	The baseline period is the screening/lead-in period prior to the day of first dose of study treatment.	
 
• Treatment period starts on the day of first dose of study treatment and ends 
 
◦ at Week 26 (Visit 23) if completed treatment and Visit 23
 
◦ on the last dose date of study treatment + 10 days for LY3209590, +1 day for glargine if discontinued study treatment early
 
 
 
• Post-treatment period starts from 
 
◦ Week 26 (Visit 23)+1 day if completed treatment and Visit 23
 
◦ last dose date of treatment +11 days for LY3209590, +2 days for glargine if discontinued study treatment early
 
 
 
 
and ends on the last date in the study

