Incidence of Level 2 hypoglycemic events: 
 
• All documented
 
	Baseline, 0-6, 0-12, 0-26, 12-26 weeks, post-treatment period	Logistic regression with treatment, baseline HbA1c and baseline Level 2 hypoglycemia incidence as covariates.
Incidence of Level 3 hypoglycemic events: 
 
• All documented
 
	Baseline, 0-26 weeks, post-treatment period	Logistic regression with treatment and baseline HbA1c as covariates.

Endpoint	Analysis Period	Statistical Method
Incidence of Level 2/3 hypoglycemic events: 
 
• All documented
 
• Nocturnal
 
• Non-nocturnal
 
	Baseline, 0-6, 0-12, 0-26, 12-26 weeks, post-treatment period	Logistic regression with treatment, baseline HbA1c and baseline hypoglycemia incidence of the same hypoglycemia type as covariates.
Potential Persistent-recurrent hypoglycemic events 
 
• Identified by investigator
 
• Identified by prespecified criteria (defined in Section 6.11)
 
	Safety analysis period (see definition in Section 4.6)	The number of participants with at least 1 event will be summarized and compared by Fisher's exact test. The number of events will also be provided. Listings of the events will also be provided.

Abbreviations: HbA1c = hemoglobin A1c; Level 2/3= Level 2 and Level 3 composite.

Note: The yearly hypoglycemia rate during defined period is calculated by number of hypoglycemic events within the period/number of days patient at risk within the period \*365.25. For rare events, 100 year rate will be provided. The hypoglycemia incidence during defined period indicates if the patient has at least 1 hypoglycemia event within the period (Yes/No).

Note: Group comparisons for hypoglycemia incidence and rate at baseline , baseline HbA1c is not included in the model.

Note: The hypoglycemia rate during the defined period is calculated by the number of hypoglycemia events within the period/number of days a participant is at risk within the period. The hypoglycemia incidence during the defined period indicates if the participant has at least 1 hypoglycemia event within the period (yes/no).

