Incidence of Level 2 hypoglycemic events ending with $\geq 70$ mg/dL: • 24-hour	Baseline, 0-4, 8-12, 22-26, 0-26 weeks, post-treatment period	Logistic regression with treatment, baseline HbA1c and baseline incidence for Level 2 hypoglycemia ending with $\geq 70$ mg/dL as covariates.

Endpoint	CGM Session*	Statistical Method
Duration of Level 1 or Level 2 hypoglycemic events: 
 
• 24-hour
 
	Baseline, 0-4, 8-12, 22-26, 0-26 weeks, post-treatment period	For 0-4, 8-12, 22-26 weeks: The MMRM model will include treatment, strata (country, routine use of personal CGM or FGM at randomization, baseline HbA1c stratum (<8.0%, ≥8.0%)), time and treatment-by-time interaction as fixed effects, and baseline duration as a covariate. For 0-26 weeks: ANCOVA model model will include treatment, strata (country, routine use of personal CGM or FGM at randomization, baseline HbA1c stratum (<8.0%, ≥8.0%)), and baseline duration. For Baseline and post-treatment period: ANOVA models only include treatment.
Duration of Level 2 hypoglycemic events: 
 
• 24-hour
 
	Baseline, 0-4, 8-12, 22-26, 0-26 weeks, post-treatment period.	Same models as for Level 1 or Level 2 hypoglycemic events. A listing will be provided for participants with Level 2 hypoglycemia episodes lasting >360 minutes
Duration of Level 2 hypoglycemic events ending with BG >=70 mg/dL: 
 
• 24-hour
 
	Baseline, 0-4, 8-12, 22-26, 0-26 weeks, post-treatment period.	Same models as for Level 1 or Level 2 hypoglycemic events.

Abbreviations: HbA1c = hemoglobin A1c.

Note: The hypoglycemic rate during defined period is a yearly rate and calculated by number of hypoglycemic events within the period/number of days patient at risk within the period\*365.25. The hypoglycemia incidence during defined period indicates if the patient has at least 1 hypoglycemic event within the period (Yes/No).

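### For the Baseline period, the hypoglycemia rate and incidence models still carry the baseline hypoglycemia covariate, so the modelled comparison adjusts the outcome for itself

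*SAP*

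**What the plan says.** In the participant-reported table (SAP Section 4.6.2.2.1), the analysis periods for most rows are "Baseline, 0-6, 0-12, 0-26, 12-26 weeks, post-treatment period"; the Level 3 rows list fewer periods but also include Baseline. One model is given per row and serves all its periods. For Level 2/3 event rates it is "Negative binomial regression with treatment, baseline HbA1c and baseline hypoglycemia rate of the same hypoglycemia type as covariates", with log exposure as offset. For Level 2/3 incidence it is "Logistic regression with treatment, baseline HbA1c and baseline hypoglycemia incidence of the same hypoglycemia type as covariates". The Level 1 and Level 2 rows follow the same pattern, and the Level 3 rate row carries the baseline Level 3 rate. Level 3 incidence is the exception: "Logistic regression with treatment and baseline HbA1c as covariates".

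A note under that table addresses the Baseline period: "Group comparisons for hypoglycemia incidence and rate at baseline , baseline HbA1c is not included in the model". It does not mention the baseline hypoglycemia covariate. SAP Section 4.1 defines a single baseline for these events: "The baseline period is the screening/lead-in period prior to the day of first dose of study treatment".

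The CGM table (SAP Section 4.6.2.2.2) also lists Baseline in every row. Its Level 2 incidence model, for example, is "Logistic regression with treatment, baseline HbA1c and baseline Level 2 hypoglycemia incidence as covariates". Its rate and incidence rows have no visible note dropping any term at baseline. Its duration rows do: for the baseline and post-treatment periods, "ANOVA models only include treatment".

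**The concern.** In the Baseline period, the baseline rate or incidence is not a prior measurement. It is the response. A model that keeps it asks whether the arms differ in baseline hypoglycemia among participants with the same baseline hypoglycemia, and that question has no content.

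At stake is the modelled check on whether the arms started level. Nocturnal Level 2/3 events, the event type behind the third key secondary endpoint, are among the rows affected. A programmer who follows the text gets failed logistic fits and rate ratios unrelated to the real difference. A programmer who does the sensible thing departs from the SAP without cover.

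**Working it through.** The documents give no figure for baseline-period comparisons, so there is nothing to reproduce. The check is a reading of the rows, an algebraic argument, and simulation for size.

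**1. Rows affected.** The participant-reported table has 4 rate rows and 4 incidence rows (Levels 1, 2, 3 and 2/3). All but Level 3 incidence carry the same-type baseline covariate: 7 of 8. The CGM table has 3 rate rows and 3 incidence rows, and all 6 carry a same-type baseline covariate. Together that is 13 of 14. In the first table baseline HbA1c drops out at baseline. In the second even that stays in, as far as the text shows.

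**2. Incidence.** Let y = 1 if the participant had an event in the baseline period. The covariate is the same y, so the model is logit P(y = 1) = a + b·treatment + c·y. For any fixed b, letting a go to minus infinity and a + c to plus infinity drives every fitted probability to the observed 0 or 1, and the likelihood tends to its maximum of 1. This is complete separation. There is no finite estimate, and the data say nothing about b. The CGM row for Level 1 or Level 2 incidence uses the baseline rate instead, but a rate above zero occurs exactly when y = 1, so it separates too. One trial fit gave coefficients of -14 and +48 with standard errors above 33,000. In the 21-day simulation below, the self-adjusted logistic model separated in 100% of runs.

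**3. Rates.** With at-risk time t and count y, the covariate is r = y/t. The model is log E(y) = log t + a + b·treatment + c·r. Once r and t are known, y = r·t exactly, so nothing is left for treatment to explain. The coefficient b only picks up the mismatch between an exponential curve in r and a quantity that is linear in r.

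**4. Size.** Common input: 335 per arm (670/2, SAP Section 5). All baseline rates and dispersions are assumptions. The pair 1.1 and 0.55 per year is borrowed from the on-treatment planning rates in SAP Section 5.

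*21-day baseline* (the 3-week screening/lead-in), dispersion 1 and 4, 300 runs each. At 1.1 per year the expected events are 1.1 × 21/365.25 × 335 ≈ 21 in one arm, against about 11 at 0.55.

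| Assumed rates per year | True ratio | Treatment only (median) | With own baseline rate (median) |
|---|---|---|---|
| 1.1 vs 0.55 | 0.50 | 0.50 | 1.00 |
| 10 vs 5 | 0.50 | 0.50 | 0.90 |

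The treatment-only logistic model was estimable, with median odds ratios of 0.49 to 0.60.

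*11 to 17 days* (the interval from Visit 2 to Visit 3, Protocol Section 1.3), assumed rates 1.1, 3 and 6 per year, 300 runs each.

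| True ratio | Treatment only (medians) | With own baseline rate (medians) |
|---|---|---|
| 1.5 | 1.51 to 1.57 | 0.97 to 1.00 |
| 2.0 | 1.98 to 2.06 | 1.00 to 1.13 |

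*Limit of both tables.* The self-adjusted fits used a log-link count model (dispersion near zero in the 21-day set), whereas the SAP specifies negative binomial. Fitting the negative binomial itself (11 to 17 days, dispersion 4, 150 runs per scenario) gave medians of 0.93 to 1.07, so the direction holds. At 1.1 per year it was unstable: the 5th to 95th percentile range was about 0.03 to 2.1 for a true 1.5 and about 0.00 to 2.4 for a true 2.0, and 22 to 23% of fits lacked convergence or finite standard errors. Those tails will shift with seed and optimiser. Only point estimates are used here, because p-values from a self-adjusted fit have no meaning.

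**The case against.** The SAP never says that the baseline hypoglycemia covariate is kept. That is inferred from a note that names HbA1c alone. The note is ungrammatical, it plainly aims to shrink the model at baseline, and the CGM duration row shows what the sponsor had in mind. A drafting omission is the likeliest explanation, and a separated logistic model would be noticed. All of this stands, and it is a reason to correct the sentence.

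A reader might infer that a chance imbalance would be hidden, or reported as balance. The documents do not support that. SAP Section 4.6 has incidence and event rate, both participant-reported and CGM-based, summarised by arm and analysis period, Protocol Section 9.3.5 plans by-arm summaries too, and Baseline is one of the SAP periods. In simulation (11 to 17 days, dispersion 4) the raw by-arm rate ratio had medians of 1.43 to 1.48 for a true 1.5 and 1.93 to 2.06 for a true 2.0, so an imbalance shows without any model.

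A reader might also infer that the count model always returns a ratio near 1. That too is more than the evidence shows: medians of 0.90 and 1.13 occurred, and at low rates single fits were scattered.

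On scope, Level 3 incidence has no hypoglycemia covariate and becomes treatment-only once the note is applied. The Level 3 rate has a covariate-free empirical fallback (SAP Appendix 11) when events are too few. The CGM column header carries an asterisk with no matching footnote in the text available, so a note there may have been lost in extraction.

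**Conclusion.** The point holds on the text. Followed literally, 13 of 14 rate and incidence rows regress the baseline outcome on itself. The failure of the incidence models is certain and needs no assumption. The failure of the rate models follows from the algebra; its size (a true twofold difference estimated at a median between 0.90 and 1.13 in the log-link fits, depending on scenario and direction) rests on assumed baseline rates and dispersion, which the documents do not give.

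The consequence is small. Only the modelled baseline comparison is wrong, and the by-arm summaries remain. It would be a mistake to carry the criticism over to the third key secondary test. That test compares rates over Weeks 0 to 26, where the baseline rate is a genuine pre-treatment covariate. No primary or key secondary conclusion changes.

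**What to change.** Replace the note under the participant-reported table with: *For the Baseline period, the models include treatment only (with the at-risk-time offset for rates); baseline HbA1c and the baseline hypoglycemia rate or incidence are not included.* Add the same sentence to the CGM table for its rate and incidence rows, so that they match the duration rows.

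The cost is one sentence in two places and a shorter model statement. It needs no new data and leaves every post-baseline analysis unchanged.
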